5 Administer first dose of study drug only after Screening/Baseline Visit procedures are completed. For participants in cohort 1, infusions occur in-person at clinic at the Screening/Baseline study visit, Week 1, Week 2, and the Week 3 study visits. Weekly infusions will continue through Week 24. An in-clinic infusion and clinic visit may occur on the same day, provided both visits are conducted in-person and within window. There should be no fewer than 4 days (96 hours) between study drug infusions.

6 Refer to the Pharmacy Manual, site policy, and GCP guidelines on site investigator responsibilities, drug accountability, compliance, and source documentation. Any and all accountability records may be requested by sponsor for review at any time.

7 The combined Screening/ Baseline visit may be split into a Screening and a Baseline visit as needed. If baseline infusion occurs on the same day as screening, it must occur after obtaining written informed consent, completing all screening procedures, and confirming participant eligibility.

8 Vital status, defined as a determination of date of death or death equivalent or date last known alive, will be determined for each enrolled participant at the end of their EAP participation (generally the Week 24 visit, as indicated). If at that time the participant is alive, his or her vital status should be determined again at the time of the last patient last visit (LPLV) of the EAP. We may also ascertain vital status at later time points by using publicly available data sources as described in section 6.6.10 of this protocol.

Mass General Brigham Institutional Review Board
Intervention/Interaction Detailed Protocol

Schedule of Activities – Cohort 2 (Platform Trial RGE Roll-over Participants)¹⁰

Activity	Screening/ Baseline Combined ^{1,8}	Week 3	Week 12	Week 24 or Early Term.	Follow-up Safety Call
	Clinic	Clinic	Telemed/ Phone	Clinic	Telemed/ Phone
	Day -21 to 0	Day 21 ±3	Day 84 ±7	Day 168 ±14	28 ±7 days after last doses
Written Informed Consent	X				
Inclusion/Exclusion Review	X				
ALS & Medical History	X				
Demographics	X				
Physical Examination ¹⁰	X				
Neurological Exam ¹⁰	X				
Vital Signs ²	X ^{1,10}	X Weekly documentation of infusion-associated vital signs			
Slow Vital Capacity (SVC) ¹⁰	X ¹			X	
ALSFRS-R	X ¹	X	X	X	
ALSAQ-40 ¹⁰	X ¹			X	
Clinical Safety Labs ³	X ¹	X		X	
Biomarker Collection (Serum) ¹⁰	X			X	
Concomitant Medication Review	X ¹	X	X	X	
Adverse Event Review	X ¹	X	X	X	X

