6.6.10 Recording Deaths and Vital Status Determination

Information on whether a participant has died may be obtained from the participant's family, from clinic notes, or from a publicly available data source like the Centers for Disease Control and Prevention (CDC) National Death Index or the Social Security Death Index.

Vital status, defined as a determination of date of death or PAV status or date last known alive and date last known to be PAV-free, will be determined by site study staff for each enrolled participant at the end of their EAP participation (generally the Week 24 visit, as indicated in the SOA). At approximately the time of the last patient last visit (LPLV) of the EAP, a second vital status check will be completed by site study staff for each enrolled participant. When prompted by the Coordination Center, sites will contact all enrolled participants to assess vital status.

We may also ascertain vital status at later time points. An outside vendor may be used to ascertain death or date of last known alive for all enrolled participants by using publicly available data sources. If prompted by the Coordination Center, sites will provide demographic information (e.g. participant name, date of birth, last known address) to the vendor using a secure method.

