10.4.4 Recording of Adverse Events

All clinical Adverse Events and Key Study Events (e.g., Mortality, Pregnancy, PAV, and Tracheostomy) are recorded in the participant’s study binder. The site should enter the AE and Key Study Event information into the EDC system as soon as possible after learning of the event or receiving an update on an existing event.

Entries on the AE Log (and into the EDC system) will include the following: description of the event, severity, seriousness, date of onset, date of resolution, relationship to investigational product, action taken, and primary outcome of event.

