3. ANALYSIS SETS

3.1 Definition of Analysis Sets

The following analysis sets are defined for this study:

Analysis Set	Definition
Screened Set	All participants who signed the informed consent form.
Full Analysis Set (FAS)	All participants who received at least one dose of Trehalose.
Per-Protocol Set (PPS)	
All participants included in FAS and who satisfy all the criteria below:
 
 - Did not have a major protocol deviation that affected the scientific integrity of the trial. - Received at least 85% and not more than 125% of the prescribed infusion volume up to the point of drug withdrawal/ last infusion. Data after drug withdrawal/ last infusion will not be included. 
The PPS will be finalized prior to the database closure.

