4.7.1.3 Sensitivity Analyses

To assess the treatment effect in OS, the following sensitivity analyses will be performed using similar approaches as described in the main analysis:

- OS comparison between PS matched (based on other caliper widths if available) Trehalose group and historical control group, including PS matched ID as stratification factor
- OS comparison between PS stratification-based Trehalose group and historical control group, including PS stratification-built strata and bulbar onset as stratification factors

Besides, for EAP study Trehalose group, the OS will also be evaluated by including the usage of permanent assisted ventilation (PAV) as event outcome together with death. A participant will be classified as having an event or being censored based on the earliest occurrence of outcomes as outlined in Table 4. The analytical approach will be the same as the approach detailed in Section 4.7.1.2.

Table 4 Censoring Rules for OS (Including PAV)

Scenario	Date of Event or Censored	Event or Censored
Usage of PAV	Date PAV started	Event
Death	Date of death	Event
Others	Date of last known to be alive	Censored

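### OS (including PAV) is censored at the last-alive date rather than the last alive-and-PAV-free date, and its historical-control comparisons name no source of PAV data

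*SAP*

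**What the plan says.** **Censoring.** SAP 4.7.1.3 introduces OS (including PAV) for the EAP trehalose group. In Table 4 the start of PAV and death are events, and the remaining row censors at "Date of last known to be alive".

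**What sites collect.** Protocol 6.6.10 defines vital status as "date of death or PAV status or date last known alive and date last known to be PAV-free". It is determined at the end of participation, and around the last patient's last visit (LPLV) "a second vital status check will be completed by site study staff for each enrolled participant". The same section adds: "An outside vendor may be used to ascertain death or date of last known alive for all enrolled participants by using publicly available data sources". The Schedule of Activities footnotes give a narrower definition with no PAV-free date: "Vital status, defined as a determination of date of death or death equivalent or date last known alive". Protocol 10.4.4 lists PAV among the Key Study Events that sites enter in the EDC.

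**Comparisons with controls.** SAP 4.7.1.4 plans three for the composite: FAS with PS stratification, PPS with PS matching, and PPS with PS stratification. It says the PPS analyses follow the approaches already set out. SAP 4.2.1 requires controls to have known mortality and ALSFRS-R and/or vital capacity data. It does not mention PAV.

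**Per-protocol data.** For the PPS, SAP 3.1 states: "Data after drug withdrawal/ last infusion will not be included".

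**The concern.** There are two separate problems.

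(a) Table 4 carries over the censoring date of death-only OS. If someone is last known PAV-free at one date and last known alive at a later one, the time between is counted as event-free although PAV could have started unseen. That overstates PAV-free survival in the EAP. The dates can separate when alive status comes from the vendor search, or from a contact at which PAV was not asked.

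(b) For controls the SAP gives no PAV data source, no requirement to be PAV-free at baseline (EAP participants are, by exclusion criterion 11), and no handling of controls without PAV data. If PAV counts as an event mainly or only in the treated group, an inert drug looks harmful.

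The two errors work in opposite directions, so a reader of the result could not sign the net bias.

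**Working it through.** The documents give no event rate, hazard ratio or power for this composite, so there is no planned figure to reproduce. The sizes below rest on **assumed** constant, independent monthly hazards: death d = 0.02; PAV p = 0.005, 0.01 or 0.02.

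**1. Where the dates can separate.** Using the SAP's 30.4375 days per month, Week 24 is 168/30.4375 = 5.5 months and a safety call 28 days later is 196/30.4375 = 6.4 months. With the Week 24 dose at its upper limit (SAP Day 183) and the call 35 days after it, the last scheduled contact is 218/30.4375 = 7.2 months. SAP 4.7.1.2 reports survival at 8 months, so that landmark always relies on the LPLV check or a later source.

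**2. Size of (a).** True 8-month event-free probability: exp(−8(d+p)). If PAV is known only to time t but alive status runs past 8 months, Table 4 estimates exp(−8d − p·t). For example, with p = 0.02 and t = 5.5: exp(−0.27) = 0.763 against exp(−0.32) = 0.726. Overstatement in percentage points (share with a gap × difference):

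| p | True | All, t=6.4 | All, t=5.5 | 20%, t=6.4 | 20%, t=5.5 |
|---|---|---|---|---|---|
| 0.005 | 0.819 | 0.66 | 1.03 | 0.13 | 0.21 |
| 0.01 | 0.787 | 1.27 | 1.99 | 0.25 | 0.40 |
| 0.02 | 0.726 | 2.36 | 3.72 | 0.47 | 0.74 |

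The largest 20% figure is 0.0074 × 70 = 0.5 of a participant. The standard error there is √(0.726 × 0.274/70) = 5.3 points, so the bias is 0.74/5.3 = 0.14 standard error. If the dates agree, the bias is zero.

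**3. Size of (b), FAS PS-stratified comparison, inert drug.** If controls capture a fraction c of PAV and the EAP has no gap, HR = (d+p)/(d+c·p).

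| c | p=0.005 | p=0.01 | p=0.02 |
|---|---|---|---|
| 0 | 0.025/0.020 = 1.25 | 0.030/0.020 = 1.50 | 0.040/0.020 = 2.00 |
| 0.5 | 0.025/0.0225 = 1.11 | 0.030/0.025 = 1.20 | 0.040/0.030 = 1.33 |
| 1 | 1.00 | 1.00 | 1.00 |

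Adding a 20% EAP gap changes the c = 0 range only to 1.24 to 1.96.

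**4. Does the censoring fix work?** It was simulated under further assumptions: uniform enrolment over 6 or 12 months, LPLV check 5.5 or 6.4 months after the last enrolment, vendor search 6 months later. Bias in 8-month event-free probability, in points:

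| Scenario | Table 4 | Row change alone | Row change + LPLV cutoff | Repeat run with public-record deaths to cutoff |
|---|---|---|---|---|
| No loss to contact | +0.04 to +0.8 | −0.1 to −1.0 | 0.0 | not needed |
| 20% lost by 6.4 months, unrelated to risk | +0.5 to +2.2 | −1.1 to −2.7 | 0.0 | −1.3 to −1.8 |
| 20% lost, both hazards doubled after loss | +0.8 to +3.3 | not assessed | +1.9 to +2.7 | −1.5 to +0.15 |

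The row change alone over-corrects: late public-record deaths still count as events while survivors are censored earlier.

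**The case against.** The strongest reply is that this is a minor gap in sensitivity and supplementary analyses. SAP 2 says there is no formal hypothesis testing, and main OS uses death only. Site staff are to determine both dates, PAV is a Key Study Event, and the vendor search is optional, so the dates should usually agree. That stands, and it makes (a) small.

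A reader might infer that Table 4 breaks a protocol rule. It does not: Protocol 6.6.10 has the PAV-free date collected but sets no censoring rule, and Protocol 9.0 defines no death-or-PAV composite. The argument against Table 4 is one of logic.

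On (b), the SAP's statement that the PPS analyses follow the earlier approaches may carry Table 4's rows to controls in two of the three comparisons. The eligibility list in SAP 4.2.1 is also open-ended, so it does not rule out applying exclusion 11. Both points stand, but neither supplies PAV data, a baseline requirement or a rule for controls without PAV data.

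A reader might also infer that the control database lacks PAV. The documents do not say, and with complete capture the distortion in step 3 disappears.

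Finally, it is tempting to apply the hazard ratios of 1.25 to 2.00 to the PPS comparisons. That is unsupported. Read literally, the PPS rule also removes EAP deaths after the last infusion, which could shrink or reverse the effect. The SAP does not say whether those deaths count.

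**Conclusion.** The concern holds and should be corrected, chiefly for (b). Table 4 uses the wrong date for a composite that needs both conditions to be known. The error is zero when the dates agree and 0.1 to 0.7 points at 8 months if 20% of participants have a gap; 3.7 points is a ceiling that requires everyone to have one. For the FAS PS-stratified comparison, an inert drug would show a hazard ratio of about 1.25 to 2.00 if controls have no PAV data, 1.11 to 1.33 with half captured, and 1.00 with full capture. For the PPS comparisons neither size nor direction can be given. All sizes depend on the assumed hazards, and those in (b) also on an unknown capture fraction. The conclusions about main OS do not change.

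**What to change.** 1. Change the last row of Table 4 to *Date last known to be alive and PAV-free* and, **in the same amendment**, apply one calendar cutoff to the composite, the LPLV site vital-status check, for deaths and survivors alike. Later public-record deaths and alive dates go to main OS only. The row must not be changed alone.
2. Censor participants lost to site contact before the cutoff at their last PAV-free date, note that this may be informative, and repeat the run counting their public-record deaths up to the cutoff. Under informative loss the cutoff alone is not clearly better than Table 4. The two runs enclosed the truth to within 0.2 points in the cases simulated, though both can slightly overstate.
3. State how PAV is recorded in the control data. In the composite comparisons use only controls with PAV status recorded and PAV-free at baseline, under the protocol's PAV definition and the same censoring rules. Re-run matching or strata and the balance checks for that pool. If PAV is not recorded, report the composite for the EAP only.

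First confirm that the EDC holds the PAV-free date; otherwise use the last site contact at which PAV was asked. The Schedule of Activities footnotes should be aligned with 6.6.10.

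**Cost.** Composite follow-up is slightly shorter. With uniform enrolment over 6 months, (6 − 2.5)/6 = 58% to (6 − 1.6)/6 = 73% of participants could be followed to 8 months by the cutoff; over 12 months, (12 − 2.5)/12 = 79% to (12 − 1.6)/12 = 87%. There may be fewer controls, and the control pool will differ from that of main OS.

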4.7.1.4 Supplementary Analyses

For OS (Including PAV), one additional comparison between PS stratification-based Trehalose group and historical control group under FAS will be provided. Besides, the following analyses will be performed for the participants in PPS, using the same approaches as described above.

- OS and OS (Including PAV) summary for EAP study by treatment cohort and overall
- OS and OS (Including PAV) comparison between PS matched (based on the pre-specified caliper width for main analysis) Trehalose group and historical control group. If the stratified analysis is invalid due to lack of event in some strata, the unstratified HR and 95% CI, as well as unstratified log-rank p-value will be provided
- OS and OS (Including PAV) comparison between PS stratification-based Trehalose group and historical control group

4.7.2 ALSFRS-R

4.7.2.1 Definition of Endpoints

The endpoint is the mean change from baseline in ALSFRS-R total score measured at Week 24.

The ALSFRS-R is a validated instrument for evaluating the levels of the functional status of participants with ALS in 4 areas, including bulbar, gross motor activity, fine motor activity, and respiratory functions. The scale includes 12 functional items, and each item is rated on a 0 to 4 scale, with a maximum total score of 48. A higher score indicates greater retention of function. The total score collected in eCRF will be used for the analysis.

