1.0 BACKGROUND AND SIGNIFICANCE

1.1 Amyotrophic Lateral Sclerosis

Amyotrophic lateral sclerosis (ALS) is a serious, life-threatening, rare degenerative disorder of large motor neurons of the cerebral cortex, brain stem and spinal cord that results in progressive wasting and paralysis of voluntary muscles [1]. The incidence of ALS is currently approximately 2/100,000/year [2,3] and may be increasing [4]. The lifetime ALS risk is 1 in 600 to 1 in 1000. Even though the incidence of ALS is similar to that of multiple sclerosis [5], the prevalence is only 4- 6/100,000 (about 25,000 patients in the United States), due to the higher mortality rate. Fifty percent of people with ALS die within three years of onset of symptoms and 90% die within five years [5]. The median age of onset is 55 years. The cause in most cases is unknown. Age and gender are the only risk factors repeatedly documented in epidemiological studies [6]. There is a slight male predominance (3:2 male to female ratio) in sporadic ALS.

No treatment prevents, halts or reverses the disease, although riluzole use is associated with a 10% prolongation of survival [7, 8], and edaravone, an antioxidant, slows illness by approximately 33% in some people [9].

The majority of people with ALS have sporadic (SALS) disease; 10% are familial (FALS). More than 100-point mutations in the gene encoding cytosolic copper-zinc superoxide dismutase (SOD1) have been demonstrated to cause typical FALS [10]. Essential features of ALS are progressive signs and symptoms of lower motor neuron dysfunction (atrophy, cramps, and fasciculations) associated with corticospinal tract signs (spasticity, enhanced and pathological reflexes) in the absence of sensory findings [3]. There is relative sparing of muscles of eye movement and the urinary sphincters. The course is relentless with decline in strength, respiratory function and overall function with time during the active phase of the disease [11]. Natural history studies have determined that age at onset, site of onset, delay from first symptom to entering ALS clinic, and rate of change in respiratory function are significant covariates of survival [12,13,14,15].

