4.1.3 Dropouts, Missing/Incomplete Data, and Outliers

Missing data occurs when any requested data is not provided, leading to blank fields on the collection instrument. These data will be indicated using a “blank” in participant listing displays. Answers such as “Not applicable” and “Not evaluable” are not considered to be missing data and should be displayed as such. In general, missing data will not be imputed unless specifically stated in this SAP.

The missing/incomplete dates for adverse events, and prior/concomitant medications, procedures (for the purpose of computing durations and treatment emergent status of adverse events, medications and procedures status (prior and/or concomitant)), ALS symptom onset date and diagnosis date will be imputed according to the rules specified in Appendix 2. Partial dates will still be displayed in listings.

Uncoded events at the time of analysis will be assigned the string “UNCODED” as the system organ class, and the reported term will be used as the preferred term so they can be included in the summary tables. In the final dataset, all the adverse events should be coded.

Uncoded medications at the time of analysis will be assigned the string “UNCODED” as the Anatomical-Therapeutic-Chemical (ATC) summary level(s) and the verbatim term will be used as the preferred name, so they can be included in the summary tables. In the final dataset, all the medications will be coded.

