4.7.2.2 Main Analytical Approach

For participants in FAS, the ALSFRS-R total score as well as the change from baseline will be summarized descriptively at scheduled visits (Baseline, Week 3, Week 12 and Week 24) by treatment group. The linear mixed-effects model for repeated measures (MMRM) will be used to calculate the least square mean for each treatment group, and the treatment difference between PS matched (based on the pre-specified caliper width for main analysis) Trehalose group vs. historical control group.

The MMRM model will include the ALSFRS-R total score change from baseline at scheduled post-baseline visits as the dependent variable, with fixed effects for treatment, bulbar onset (Yes/No) and baseline value, visit (as categorical variable), treatment-by-visit interaction, and baseline value-by-visit interaction, with visit as the repeating factor, participant as a random effect. PS matched ID will also be included as a random effect for comparison between Trehalose group vs. historical control group.

The MMRM model will use restricted maximum likelihood (REML) to estimate least squares means and treatment differences. An unstructured covariance matrix will be used to model within-participant errors. Data

from all scheduled visits over the treatment period will be used to fit the model. Missing data will not be imputed.

If the computational algorithm fails to converge, the following structures will be executed in the order specified until convergence is achieved: Toeplitz with heterogeneity (TOEPH), autoregressive with heterogeneity (ARH(1)), compound symmetry with heterogeneous variances (CSH), autoregressive (AR(1)), Toeplitz (TOEP), and compound symmetry without heterogeneous variances (CS).

At the post-baseline visits of Week 3, Week 12 and Week 24, the least square mean and standard error (SE), as well as 2-sided 95% CI for each treatment group will be provided. The difference (SE) and 95% CI, p-value between PS matched Trehalose group and historical control group will be summarized.

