4.7.2.4 Supplementary Analyses

The following analyses will also be performed for the participants in PPS, using the same approaches as described above.

- ALSFRS-R total score summary for EAP study by treatment cohort and overall
- ALSFRS-R total score comparison between PS matched (based on the pre-specified caliper width for main analysis) Trehalose group and historical control group
- ALSFRS-R total score comparison between PS stratification-based Trehalose group and historical control group

In addition, an analysis of the total ALSFRS-R score will be performed using a general linear mixed effects model to compare the rate of decrease (ie, slope) of total ALSFRS-R scores over the 24-week treatment period between the PS matched (based on the pre-specified caliper width for main analysis) Trehalose and historical control, and between the PS stratification based Trehalose and historical control, respectively, for both FAS and PPS.

The model will fit a random intercept and slope for each participant and will include fixed effects for treatment group, bulbar onset (Yes/No), visit, and treatment by visit interaction. For comparison between the PS matched Trehalose and historical control, PS matched ID will be included as random effect; for comparison between PS stratification-based Trehalose and historical control, the PS stratification-built strata will be included as fixed effect.

An unstructured covariance structure will be used to model the within-participant errors. Visit will be expressed in weeks as a continuous variable and will include all scheduled visits including baseline as Week 0 (i.e., Week 0, Week 3, Week 12, Week 24). Missing values will not be imputed.

Estimates of the slope will be presented by the treatment group along with corresponding 95% CIs. The estimate of the difference between slopes (Trehalose vs. historical control) and the 95% CI of the difference between slopes will be presented. The null hypothesis of no difference in slopes between the treatment groups will be determined by testing the significance of the treatment by visit interaction term.

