4.7.3 SVC

4.7.3.1 Definition of Endpoints

The endpoint is the mean change from baseline in % predicted SVC (or VC) at Week 24.

For this EAP study, the SVC is measured at Screening/Baseline and Week 24 visit with the 3 best trials recorded on the eCRF. The % predicted SVC value will be calculated at each visit for analysis following the calculation algorithm in Appendix 3. For historical control group, the % predicted VC (based on collected SVC or FVC) will be used.

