4.7.3.2 Main Analytical Approach

For participants in FAS, the % predicted SVC (or VC) as well as the change from baseline will be summarized descriptively at Baseline and Week 24 by treatment group.

For EAP study treatment groups, an analysis of covariance (ANCOVA) model with change from baseline at Week 24 as the dependent variable, including main effects for treatment group, bulbar onset (Yes/No) and baseline value will be performed. The % predicted SVC change from baseline's least square mean (SE) and 2-sided 95% CI for each treatment group will be provided at Week 24.

For comparison between PS matched (based on the pre-specified caliper width for main analysis) Trehalose group vs. historical control group, a linear mixed effects model will be used, including the % predicted VC change from baseline at Week 24 as the dependent variable, with fixed effects for treatment group, bulbar onset (yes/no), and baseline value, with propensity score matched ID as the random effect. At Week 24, the % predicted vital capacity change from baseline's least square mean (SE) and 2-sided 95% CI for PS matched Trehalose and historical control groups will be presented. The difference (SE) and 95% CI, p-value for PS matched Trehalose vs. historical control will be summarized.

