For ALSAQ symptom index and each subscale, the score and change from baseline will be summarized descriptively at Baseline and Week 24 for EAP study treatment groups for FAS. At week 24, the least square mean (SE) and 2-sided 95% CI for each treatment group will be provided using the analysis of covariance (ANCOVA) model with change from baseline at Week 24 as the dependent variable, including main effects for treatment group, bulbar onset (Yes/No) and baseline value as covariate.

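### The matched ALSFRS-R and vital-capacity comparisons treat death before Week 24 as ordinary missing data, which tilts the functional difference towards whichever group has more deaths

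*SAP*

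**What the plan says.** - **ALSFRS-R (SAP 4.7.2.1, 4.7.2.2).** "The endpoint is the mean change from baseline in ALSFRS-R total score measured at Week 24". The main analysis is an MMRM on Weeks 3, 12 and 24, and "Missing data will not be imputed". The supplementary random-slope model (4.7.2.4) uses all scheduled visits and has the same rule: "Missing values will not be imputed".
- **Vital capacity (SAP 4.7.3.1, 4.7.3.2).** "The endpoint is the mean change from baseline in % predicted SVC (or VC) at Week 24". Within the EAP the model is "an analysis of covariance (ANCOVA) model with change from baseline at Week 24 as the dependent variable". The matched comparison with controls is a separate linear mixed model, also on the Week 24 change alone.
- **ALSAQ-40 (SAP 4.7.4).** An ANCOVA for the EAP groups only, with "change from baseline at Week 24 as the dependent variable, including main effects for treatment group, bulbar onset (Yes/No) and baseline value as covariate". Table 5 covers missing items, not death.
- **General rule (SAP 4.1.3).** "In general, missing data will not be imputed unless specifically stated in this SAP". None of the stated exceptions concerns death.
- **Sensitivity and supplementary analyses (4.7.2.3, 4.7.2.4, 4.7.3.3, 4.7.3.4).** They vary the caliper, propensity stratification or analysis set, or add the slope model. None combines function with survival.
- **Death.** It is analysed as overall survival (4.7.1), which Protocol 9.0 places ahead of ALSFRS-R and SVC.
- **Who enters.** Controls need a post-baseline ALSFRS-R and/or VC measurement (SAP 4.2.1). The FAS needs only one dose (SAP 3.1).

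**The concern.** In ALS, death is the end of functional decline, not a chance gap in the data. The MMRM and slope model use a participant's earlier visits and in effect carry the expected trajectory on past death. Two early visits reveal an individual's slope only in part, so some of the link between fast decline and death stays uncorrected. The VC model has a single post-baseline time point, so it compares only those who reach it.

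If the groups differ in mortality, the functional contrast is then partly a contrast between different survivors. More deaths among fast decliners make a group look functionally better, and fewer deaths make it look worse. These contrasts carry p-values, and SAP 1 says the results might go into a regulatory submission.

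**Working it through.** **1. Expected deaths.** The documents give no expected 24-week mortality. The only power figure concerns NfL and has no bearing here. Protocol 1.1 says: "Fifty percent of people with ALS die within three years of onset of symptoms and 90% die within five years". Assuming a constant hazard h over 168/365.25 = 0.460 years, the proportion dying is 1 − exp(−0.460h):

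| Hazard taken from | h per year | Dead by Week 24 | Of 70 |
|---|---|---|---|
| First 3 years | ln 2 / 3 = 0.231 | 10.1% | about 7 |
| 5-year average | ln 10 / 5 = 0.461 | 19.1% | about 13 |
| Years 3 to 5 | ln(0.5/0.1) / 2 = 0.805 | 30.9% | about 22 |

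A Weibull curve through both points gives 7%, 15%, 24% and 33% for entry at 1, 2, 3 and 4 years from onset. The 6-month life-expectancy criterion (Cohort 1 only) and the exclusion of permanent assisted ventilation push these down. Long disease duration at entry pushes them up.

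**2. Direction and size.** All simulation inputs are assumptions: 60 per group, mean slope −1.0 points/month (SD 0.7), log hazard of death +1.2 per point/month faster decline, residual SD 1.5, visits at Weeks 3, 12 and 24. There is no functional effect, and the hazard of death is doubled on trehalose. The Week 24 differences below should be zero; positive favours trehalose.

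| Deaths, control v trehalose | MMRM | Survivors only |
|---|---|---|
| 11% v 20% | +0.22 | +0.31 |
| 19% in controls, hazard doubled | +0.35 | +0.48 |
| 25% v 41% | +0.47 | +0.60 |

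The standard error of the MMRM difference is about 0.8. A false significant benefit occurs in about 8% of trials at 40% v 24% deaths and about 4% at 10% control mortality (nominal 2.5%).

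A second set of assumptions (slope SD 0.8, log hazard +1.2 per SD, large samples) gives:
- 10% v 20% deaths: +0.29 (MMRM) and +0.42 (Week 24 ANCOVA in survivors).
- 20% v 31%: +0.43 and +0.57.
- 10% v 31%, an extreme contrast: +0.73 and +1.00.
- Equal mortality, or death unrelated to slope: within 0.1 of zero.

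The survivors-only column mirrors the structure of the VC model, but it is in ALSFRS-R points. It does not size the bias in % predicted VC.

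**3. A joint rank, and its entry condition.** With the hazard doubled from 24% mortality, a joint rank gives trehalose a win probability of 0.44, the right direction. The uneven entry rule can produce nearly the same figure with no drug effect. Let p be the proportion dying by Day 168 among those who enter, and count pairs in which both die or both survive as even. The win probability is then (1 − p_T)p_C + ½(1 − p_T)(1 − p_C) + ½p_T·p_C = ½ + (p_C − p_T)/2.

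Take 24% mortality in both groups at constant hazard: −ln(0.76)/168 = 0.00163 per day. Deaths by Day 21 are 3.4% and by Day 91 13.8%.
- Controls must survive to a first follow-up at about 3 months (assumed), trehalose enters on one dose: p_C = (24 − 13.8)/86.2 = 11.8%, p_T = 24%, win probability 0.44. Full simulation gives 0.43, with significant false harm in 26% of trials.
- Trehalose must have its own first post-baseline visit (Week 3): p_T = (24 − 3.4)/96.6 = 21.3%, win probability 0.45. A nominally equal rule does not cure the problem if the visits fall at different times.
- Both groups must reach the same day: p_C = p_T, win probability 0.50. Simulation gives 0.50, with false harm in 3%.

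**The case against.** The strongest reply is that survival is not neglected. It is the first-priority efficacy measure. SAP 4.7.1.2 gives deaths by group, Kaplan-Meier rates including 6 months, a hazard ratio and a log-rank test in the same matched set. Sections 4.7.1.3 and 4.7.1.4 add permanent assisted ventilation, and 4.9.2 tabulates fatal events. At 40% v 24% deaths, an unstratified log-rank test detects the harm in 47% of simulated trials and a joint rank in 22%. A reader might infer that fatal harm is hidden or would pass as benefit; the documents do not support that. What stands is narrower: the functional estimate can point the wrong way, and nothing beside it warns the reader.

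Other limits also stand. The ALSFRS-R models use earlier visits, so it is wrong to say that deaths simply drop out of them. ALSAQ-40 has no control comparison, so it is affected only as a survivor-only summary within the EAP. SAP 2 calls all analyses descriptive and p-values mainly exploratory. The table shells are in a separate Data Presentation Plan that is not available and may show some of what is asked for. Overall survival shares the uneven entry rule, so it is not a clean reference either.

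**Conclusion.** The gap is real and moderate. In the matched ALSFRS-R and VC comparisons, death before Week 24 has no rule, and no planned analysis joins function with survival. With a doubled hazard of death concentrated in fast decliners, the bias is about 0.2 to 0.5 points by MMRM, roughly a quarter to a little over half of its standard error, and 0.3 to 0.6 in survivors only. It vanishes if mortality is equal or unrelated to rate of decline.

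The slopes, their spread and the hazard link are all assumed. A reader might take 10% to 31% as the plan's own mortality forecast. It is not: it applies a constant hazard to general figures counted from symptom onset. The change is worth making because it is cheap, but it does not invalidate the planned models.

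**What to change.** Keep the MMRM, slope and VC models as planned, and make these additions.

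1. **Supplementary joint rank (SAP 4.7.2.4 and 4.7.3.4)** within propensity-matched pairs in the FAS. Deaths by Day 183, the upper limit of the Week 24 window in Table 3, rank lowest in order of death time. Survivors then rank by change in function.
2. **The same entry condition in both groups, applied before matching.** SAP 4.2.1 already asks controls for a post-baseline measurement, so ask it of trehalose participants too. Tie it to a common day: alive at that day, with a post-baseline measurement by then. Choose the day from the controls' visit schedule before outcomes are compared. For VC use the ALSFRS-R measurement for this condition, because the EAP schedules post-baseline SVC only at Week 24 or early termination; a VC-based condition would remove most EAP deaths. Deaths before the common day are reported in the survival analysis.
3. **A rule for participants alive without a Week 24 value.** For example, for ALSFRS-R compare change up to the latest visit that both members of the pair have. For VC, which Protocol 6.2.1 lets some remote participants omit, use multiple imputation among survivors.
4. **Reporting.** Show deaths by Week 24 per group beside every Week 24 least-squares mean, including ALSAQ-40, and state that the MMRM estimates function as if no one died.

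The cost is SAP wording and one more exploratory analysis per endpoint on data already collected. If the drug affects function only, the simulated joint rank has slightly less power than the MMRM (44–48% v 47–52%). If it helps both function and survival (+0.3 points/month, hazard ratio 0.6), it has more (65% v 40%). Those power figures come from an unpaired rank test without the entry condition, so they are indicative only.
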